APPENDIX IV - Acceptable Contraceptive Methods

- Male or female condom with or without spermicide
- Cervical cap, diaphragm or sponge with spermicide

Highly Effective Contraceptive Methods That Are User Dependent ^a

Failure rate of <1% per year when used consistently and correctly.

- Combined (estrogen- and progesterone-containing) hormonal contraception ^b
 - Oral
 - Intravaginal
 - Transdermal
 - Injectable
- Progestogen-only hormonal contraception ^b
 - Oral
 - Injectable

Highly Effective Methods That Have Low User Dependency

Failure rate of <1% per year when used consistently and correctly.

- Progesterone-only contraceptive implant ^{b, c}
- Intrauterine hormone-releasing system (IUS) ^b
- Intrauterine device (IUD)
- Bilateral tubal occlusion

• Vasectomy

Vasectomy is a highly effective contraception method provided that the partner is the sole male sexual partner of the female of childbearing potential and the absence of sperm has been confirmed. If not, an additional highly effective method of contraception should be used.

• Sexual abstinence

Sexual abstinence is considered a highly effective method only if defined as refraining from heterosexual intercourse during the entire period of risk associated with the study treatment. The reliability of sexual abstinence needs to be evaluated in relation to the duration of the study and the preferred and usual lifestyle of the participant.)

Notes:

Use should be consistent with local regulations regarding the use of contraceptive methods for participants of clinical studies.

a) Typical use failure rates are lower than perfect-use failure rates (i.e., when used consistently and correctly).

b) If hormonal contraception efficacy is potentially decreased due to interaction with study treatment, condoms must be used in addition to the hormonal contraception during the treatment period and for at least 120 days, (corresponding to time needed to

eliminate study treatment plus 30 days for study treatments with genotoxic potential)
after the last dose of the study treatment.

c) If locally required, in accordance with Clinical Trial Facilitation Group (CTFG) guidelines,
acceptable hormonal contraceptives are limited to those which inhibit ovulation.

APPENDIX V - New York Heart Association (NYHA) Classification

NYHA Grading		MET*
Class I	No limitations. Ordinary physical activity does not cause undue fatigue, dyspnea or palpitations (asymptomatic LV dysfunction)	>7
Class II	Slight limitation of physical activity. Ordinary physical activity results in fatigue, palpitation, dyspnea or angina pectoris (mild Congestive Heart Failure (CHF)).	5
Class III	Marked limitation of physical activity. Less than ordinary physical activity leads to symptoms (moderate CHF)	2 – 3
Class IV	Unable to carry on any physical activity without discomfort. Symptoms of CHF present at rest (severe CHF).	1.6

*MET (metabolic equivalent) is defined as the resting VO_2 for a 40-year-old 70kg man.
1 MET = 3.5 mL O_2 /min/kg body weight.

APPENDIX VI - Study Drug Diaries

VENETOCLAX DRUG DIARY

Instructions:

You will use this diary to record each dose of venetoclax that you take. You should also use this diary to record any side effects that you experience and medications that you take other than the venetoclax. Please be sure to bring this diary with you to your next clinic visit.

Venetoclax:

- Venetoclax is taken once a day every day, approximately 24 hours apart.
- Venetoclax should be taken with food. On days 1 – 4 of cycle 1 it is recommended that venetoclax is taken approximately one hour after start of APR-246 infusion. Starting at cycle 2 venetoclax can be taken before or after start of APR-246 infusion (\pm 2 hours).
- If you forget to take a dose of venetoclax and it is within 12 hours of when it should have been taken, you should take the dose. If it has been more than 12 hours, you should skip that dose and take the next dose at the next regular time.
- If you vomit after taking a dose of venetoclax, you should not make up the dose or take additional pills, you should take the next dose at the next regular time.
- Always bring your pill bottles (including those that are empty) and your diary with you to each clinic visit.

If you have any questions, please ask a study team member or your doctor.

Patient Number: _____

STUDY STAFF USE ONLY

Patient Initials: _____

Staff member reviewing diary at end of study
cycle:

Cycle Number: _____

Start Date: _____

Venetoclax tablets to take at each dose: 100 mg = _____

Other information/Comments:

VENETOCLAX DRUG DIARY (continued)

Patient Number/Initials: _____ Cycle: _____

Cycle Day	Date Taken	Time Taken	Number of 100mg venetoclax tablets taken	Comments (Side effects, complaints, other medications)
1				
2				
3				
4				
5				
6				
7				
8				
9				
10				
11				
12				
13				
14				
15				
16				
17				
18				
19				
20				
21				
22				
23				
24				
25				
26				
27				
28				

* NOTE: Add additional days in case needed due to scheduling delay or dose modifications.

APPENDIX VII - Patient Handout: Prohibited Medications (For Patients Enrolled in Cohorts with Venetoclax)

PROHIBITED MEDICATIONS

APPENDIX VIII - Dose Modifications for Use with CYP3A and P-gp Inhibitors

Concomitant use of venetoclax with *strong* CYP3A inhibitors at initiation and during ramp-up phase is contraindicated. Concomitant use of venetoclax with strong CYP3A inhibitors increases venetoclax exposure (i.e., C_{max} and AUC) and may increase the risk for TLS at initiation and during ramp-up phase. For patients who have completed the ramp-up phase and are on a steady daily dose of venetoclax, reduce the venetoclax dose by at least 75% when *strong* CYP3A inhibitors must be used concomitantly.

Avoid concomitant use of venetoclax with *moderate* CYP3A inhibitors or P-gp inhibitors. Consider alternative treatments. If a moderate CYP3A inhibitor or a P-gp inhibitor must be used, reduce the venetoclax dose by at least 50%. Monitor these patients more closely for signs of toxicities.

Resume the venetoclax dose that was used prior to initiating the CYP3A inhibitor or P-gp inhibitor 2 to 3 days after discontinuation of the inhibitor.

The recommendations for managing drug-drug interactions are summarized in the table below.

Co-administered drug	Initiation and Ramp-Up Phase	Steady Daily Dose (After Ramp-Up Phase)
Posaconazole	Day 1 – 10 mg Day 2 – 20 mg Day 3 – 50 mg Day 4 – 70 mg	Reduce venetoclax dose to 70 mg.
Other strong CYP3A inhibitor	Day 1 – 10 mg Day 2 – 20 mg Day 3 – 50 mg Day 4 – 100 mg	Reduce venetoclax dose to 100 mg.
Moderate CYP3A inhibitor	Reduce the venetoclax dose by at least 50%	
P-gp inhibitor		

Warfarin

Concomitant use of venetoclax increases warfarin C_{max} and AUC_{inf} , which may increase the risk of bleeding. Closely monitor international normalized ratio (INR) in patients using warfarin concomitantly with venetoclax.

P-gp Substrates

Concomitant use of venetoclax increases C_{max} and AUC_{inf} of P-gp substrates, which may increase toxicities of these substrates. Avoid concomitant use of venetoclax with a P-gp

substrate. If a concomitant use is unavoidable, separate dosing of the P-gp substrate at least 6 hours before venetoclax.

Please refer to the venetoclax USPI³⁷ for additional details on drug-drug interactions.

Below (Table 13) are examples of CYP3A inhibitors and inducers (strong and moderate); however, this is not an exhaustive list.

Table 13. CYP3A Inhibitors and Inducers¹	
CYP3A Inhibitors	
Strong CYP3A Inhibitors	Moderate CYP3A Inhibitors
boceprevir, cobicistat, danoprevir and ritonavir, elvitegravir and ritonavir, indinavir and ritonavir, itraconazole, ketoconazole, lopinavir and ritonavir, paritaprevir and ritonavir and (ombitasvir and/or dasabuvir), posaconazole, ritonavir, saquinavir and ritonavir, telaprevir, tipranavir and ritonavir, telithromycin, troleandomycin, voriconazole	aprepitant, ciprofloxacin, conivaptan, crizotinib, cyclosporine, diltiazem, dronedarone, erythromycin, fluconazole, fluvoxamine, imatinib, tofisopam, verapamil
CYP3A Inducers	
Strong CYP3A Inducers	Moderate CYP3A Inducers
apalutamide, carbamazepine, enzalutamide, mitotane, phenytoin, rifampin, St. John's wort	bosentan, efavirenz, etravirine, phenobarbital, primidone

Note: In addition to the medications listed above, patients taking venetoclax should not consume grapefruit, grapefruit products, Seville oranges, (including marmalade containing Seville oranges), or star fruit.

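### Appendix VIII both contraindicates strong CYP3A inhibitors during venetoclax ramp-up and gives doses for that combination

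*Combined protocol and SAP*

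**What the plan says.** Appendix VIII opens with a prohibition that carries no exception: venetoclax with strong CYP3A "inhibitors at initiation and during ramp-up phase is contraindicated". The next sentence gives the reason: the combination raises venetoclax exposure "and may increase the risk for TLS at initiation and during ramp-up phase". Once ramp-up is over and the daily dose is steady, the text allows a strong inhibitor if it is unavoidable; sites must then "reduce the venetoclax dose by at least 75% when" one is used.

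The appendix continues: "The recommendations for managing drug-drug interactions are summarized in the table below". That table has one column for initiation and ramp-up and one for the steady daily dose. In the ramp-up column the posaconazole row reads "Day 1 – 10 mg Day 2 – 20 mg Day 3 – 50 mg Day 4 – 70 mg", and the row for any other strong CYP3A inhibitor reads "Day 1 – 10 mg Day 2 – 20 mg Day 3 – 50 mg Day 4 – 100 mg". The steady-dose entries are 70 mg and 100 mg.

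Table 13 in the same appendix includes posaconazole among the strong inhibitors ("posaconazole, ritonavir, saquinavir and ritonavir, telaprevir, tipranavir and ritonavir, telithromycin, troleandomycin, voriconazole"). The appendix also refers the reader to the venetoclax prescribing information "for additional details on drug-drug interactions".

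**The concern.** The sentence and the table address the same drugs on the same days and give opposite instructions. A site that opens the appendix for a patient already on a strong inhibitor at the start of venetoclax finds a prohibition and a dosing schedule on one page, for the period in which the appendix itself warns of TLS. One site may withhold the combination and another may give it, and either could be told that it departed from the protocol.

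The situation is foreseeable. Section 4.1 describes neutropenia as common in these patients, and Table 6 asks sites to consider antifungal prophylaxis while it lasts. Table 13 names five azole antifungals: four as strong inhibitors (itraconazole, ketoconazole, posaconazole, voriconazole) and one as moderate (fluconazole). That list is described as incomplete and says nothing about how often each drug is used.

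**Working it through.** No planned sample size, power or error rate is involved. The check compares the Appendix VIII text with each table cell, then asks whether the body of the protocol decides between them.

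**Step 1: inputs.** The full venetoclax dose is 400 mg. The standard ramp-up without an antifungal is 100, 200 and 400 mg on Days 1–3, then 400 mg from Day 4 (Section 6.1.2). The adjusted doses come from the Appendix VIII table.

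**Step 2: cell by cell.** Reduction = 1 − adjusted dose / standard dose.

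| Cell | Text | Table | Result |
|---|---|---|---|
| Posaconazole, ramp-up | Contraindicated | 10/20/50/70 mg | Conflict |
| Other strong inhibitor, ramp-up | Contraindicated | 10/20/50/100 mg | Conflict |
| Posaconazole, steady dose | Cut of 75% or more | 70 mg: 1 − 70/400 = 82.5% | Agree |
| Other strong inhibitor, steady dose | Cut of 75% or more | 100 mg: 1 − 100/400 = 75% | Agree |
| Moderate or P-gp inhibitor | Cut of 50% or more | Cut of 50% or more | Agree |

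The text and table disagree only in the two strong-inhibitor ramp-up cells, which hold eight daily doses in all.

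**Step 3: is posaconazole an exception?** No. Table 13 lists it as strong, and the label of the next row (other strong inhibitors) treats it as one. Even if it were exempt, that next row would still conflict.

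**Step 4: how the table doses compare with the standard ramp-up.**

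- Day 1: 1 − 10/100 = 90%
- Day 2: 1 − 20/200 = 90%
- Day 3: 1 − 50/400 = 87.5%
- Day 4: 1 − 70/400 = 82.5% with posaconazole; 1 − 100/400 = 75% with another strong inhibitor

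The table doses are therefore 75% to 90% below standard. The open question is whether to combine the drugs at all.

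**Step 5: does the body decide?**

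- Sections 4.3.2 and 6.1.2 leave the ramp-up dose with a prophylactic antifungal to local practice and the current label, and point to Appendix VIII. Section 7.2.2.1 repeats the rule without that pointer. This fits the table. It can also be met with a moderate inhibitor such as fluconazole under the 50% rule.
- Section 6.4 names strong inhibitors but not the treatment phase, so the reduction after ramp-up would satisfy it. Its paragraph ends with a reference to Appendix VIII.
- Section 6.3.10 speaks of antifungals in general, without inhibitor strength or phase.
- Section 6.3.8 sends the reader to the prescribing information.

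None of these says whether the sentence or the table prevails.

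**The case against.** The strongest reply is that the documents come closer to an answer than the appendix alone suggests. The body repeatedly names local practice and the current prescribing information as the source for dosing, so a site knows where to look. Sections 4.3.2 and 6.1.2 foresee an adjusted ramp-up with an antifungal, and the only day-by-day schedules in Appendix VIII are the two disputed cells. The alternative reading through a moderate inhibitor is weaker, because the appendix also advises against moderate inhibitors where there is another choice. It is fair to say that the body leans toward the table. A lean is not a precedence rule, though, and the cross-references bring the site back to the page that contradicts itself.

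The second reply is that the consequence is small: the table doses are well below standard, both lead-in cohorts have finished DLT review with no DLTs, and nothing statistical depends on the point. That is correct, and it limits the weight of the finding. It does not make two opposite dosing instructions acceptable.

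The third concerns TLS monitoring. The scheduled checks are 6–8 h and 24 h after the first venetoclax dose (Table 8, footnote p; Section 7.2.2.1), so none follows the Day 3 or Day 4 doses. That is true for every venetoclax patient, including those on the standard ramp-up. It is a separate monitoring choice and not a result of this conflict.

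Finally, neither the prescribing information nor the content of the Appendix VII patient handout was available for this review. Either might indicate the intended rule, but neither would remove the contradiction in Appendix VIII.

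**Conclusion.** The appendix is wrong as written and should be corrected. One sentence contradicts two table cells: with a strong CYP3A inhibitor on Days 1–4, the sentence permits no venetoclax and the table permits 10/20/50/70 mg or 10/20/50/100 mg.

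Confidence that the conflict exists is high. Which rule was intended cannot be decided from the available text. With both lead-in cohorts past dose-finding, the point bears on patients in expansion cohorts 1–4 who take a strong inhibitor during Cycle 1 ramp-up; cohort 5 receives no venetoclax. The number affected is not stated and no estimate is offered. Endpoints, sample size, the recommended Phase II dose and the planned analyses are unaffected.

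**What to change.** The sponsor's clinical team should confirm the intended rule against the current venetoclax prescribing information, to which the protocol already defers, and then make one of two edits.

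- **(a) If the table is intended:** replace the opening sentence of Appendix VIII with a statement that strong CYP3A inhibitors may be used during venetoclax initiation and ramp-up only on the reduced schedule in the table and with the TLS monitoring already specified. This changes one sentence in one appendix.
- **(b) If the prohibition is intended:** replace the two strong-inhibitor ramp-up cells with *Contraindicated*, and add a line to Sections 4.3.2, 6.1.2, 6.4 and 7.2.2.1 that strong inhibitors may start only after ramp-up. This changes two cells and adds four short clarifications.

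Until this is settled, sites should be told to contact the Medical Monitor before combining a strong inhibitor with venetoclax in ramp-up. The Appendix VII handout should be checked for the same point. Either option needs a short notice to sites. Neither changes the design, sample size or analysis.
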